### 12.3 Statistical Methods

Given the randomized stepped wedge design, we will report our results according to CONSORT guidelines. Our comparative analyses between the intervention and usual care (control) groups will employ the intent-to-treat principle. We will generate descriptive statistics (means, standard deviations, quantiles for continuous variables; counts/percentages for categorical variables) and schematic plots.

We will compare the intervention and usual care groups on salient variables in order to assess balance in the distributions of these variables. Variables found to differ between the study groups will be further evaluated to assess their confounding effects of intervention vs. usual care differences on primary and secondary outcomes. Given the nature of the cluster randomization employed, we will employ statistical analytic methods that take the correlated nature of the data into account.

Our primary analysis will use multiple logistic regression models to compare the proportion of patients with *timely initiation of treatment* across study groups, adjusting for the influence of race, language barriers to care, insurance status (private vs public), and other covariates that may have a significant effect on the outcome and may be unbalanced across the two study groups.

- To examine heterogeneity in intervention effect, exploratory analyses using multiple logistic regression interaction models will examine whether the effect of the TRIP intervention vary by three covariates of interest:
  - patient race
  - patient preferred language
  - insurance status
- Study groups will also be compared on the secondary clinical outcome of *time to initiation of primary cancer treatment* (the number of days from diagnosis to start of treatment) through Kaplan-Meier survival curves (unadjusted analyses) and Cox proportional hazards regression models controlling for cancer site and other covariates (adjusted analysis).
- *Receipt of quality care* will be analyzed through logistic regression.

For the analysis of the rate of missed appointments, patients will differ on the number of scheduled appointments over the study period. The odds of missing an appointment will be analyzed through generalized estimating equation (GEE) logistic regression models for repeated measures (appointments within patient) dichotomous data.

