### 5.1.4 Study subjects

All adult females (18 years or older) with a new breast cancer diagnosis receiving or planning to receive care at a participating site during the study period will be eligible for inclusion if they have a residential ZIP code within a 35 mile radius of Boston and have any of the following risk factors for delays in care: are Black and/or Hispanic ethnicity, speak Non-English as their primary language, and/or have only public or no form of health insurance. Based on MA Cancer Registry statistics, **1,300** study subjects are expected over the study period (633 controls, 667 intervention) as outlined below in table 6.

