### **12.2 Sample Size Determination**

Sample size estimates assume 80% power and a two-sided alpha of 0.05 for cross-sectional stepped wedge studies comparing intervention to usual care in two-group statistical analyses. This method incorporates information on the number of steps used in the stepped wedge design, the number of subjects per time period, and the degree of clustering via the intra-class correlation coefficient (ICC) to compute the design effect. A sample size of 220 subjects per

group in a log rank test will provide 80% power at a two-sided alpha of 0.05 to detect a difference in the proportion of subjects with treatment at time,  $t$ , of 81% in the intervention group compared to 70% in the usual care group, a level estimated from recent data from the clinical sites for the planned study.

This difference yields a hazard ratio of 1.75, a clinically meaningful effect size for time-to-treatment post-diagnosis. Based on our planned number of steps, enrollment per study period, and a reasonable ICC of 0.1, the design effect is 2.29. Thus, we will need to enroll and follow at least 1,008 subjects to provide 80% power for analysis of intervention effectiveness. Our planned sample size of 1,300 women will therefore provide more than adequate power to test our primary outcome.

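### Beyond race, language and insurance, the primary model's covariates are to be chosen from observed imbalance with no list or criterion, and clinical site and calendar time are not named

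*Combined protocol and SAP*

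**What the plan says.** Section 12.3 opens its comparative analysis with a balance check on variables it does not name, and continues: "Variables found to differ between the study groups will be further evaluated to assess their confounding effects". The primary model follows: "Our primary analysis will use multiple logistic regression models to compare the proportion of patients with" timely initiation of treatment, "adjusting for the influence of race, language barriers to care, insurance status (private vs public". No balance condition is attached to those three adjusters. The same sentence then adds "other covariates that may have a significant effect on the outcome and may be unbalanced across the two study groups".

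The section does not list these other covariates. It does not say what counts as differing, which test or level would be used, how confounding would be judged, or when the choice would be made. It promises methods that allow for correlation within clusters, but it names neither clinical site nor calendar time as a term in the primary model.

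**The concern.** The two groups are not individually randomised, and they differ in at least three ways that can be read from the protocol before any data arrive.

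- **Calendar time.** Control data start in August 2016 and end at a site-specific date; intervention quarters run into 2021 (5.1.1, Table 4).
- **Case finding.** Controls come from tumour-registrar lists (10.1.5). Intervention women are found by navigators through referrals, tumour boards and appointment-based lists (9.1, 9.3.4).
- **Site mix.** Table 6 projects different shares of each arm by site.

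In such a comparison a covariate should be adjusted for because it predicts time to treatment, or because the design ties it to the arm. A balance screen answers another question: its result depends on sample size and takes no account of how strongly the covariate predicts the outcome. A modest imbalance in a strong predictor can go unflagged and stay in the estimate. With no list or criterion, the primary model beyond the three named covariates is also undetermined, so two analysts following 12.3 could fit different models.

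**Working it through.** **Inputs from the documents.** 633 control and 667 intervention women (5.1.4, Table 6). Planned proportions treated by time t: "81% in the intervention group compared to 70% in the usual care group" (12.2). Design effect 2.29 (12.2).

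**Assumptions, not in the documents.** A two-sided 0.05 balance test (12.3 states no level). Outcome odds ratio of 2 per SD of the confounder, with 1.5 and 3 as a range. Application of the 2.29 design effect to a covariate; the plan derives it for the outcome, so results are shown with and without it.

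**Plan's own figure.** 2 x 220 x 2.29 = 1,007.6, which rounds up to the stated 1,008. The design effect is used as given.

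**Step 1: chance that a true imbalance is flagged.** For a standardised difference d, SE = sqrt[DE x (1/633 + 1/667)] = 0.0555 with DE = 1, and 0.0840 with DE = 2.29. The chance of a flag is Φ(d/SE − 1.96); the opposite tail is negligible.

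| Imbalance (SD) | Flagged, DE = 1 | Flagged, DE = 2.29 |
|---|---|---|
| 0.10 | 44% | 22% |
| 0.15 | 77% | 43% |
| 0.20 | 95% | 66% |
| 0.25 | 99.5% | 84% |

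The even-odds point is 1.96 x SE: 0.109 SD, or 0.165 SD with the design effect. At a more lenient 0.20 level, 0.10 SD is flagged 70% of the time (46% with the design effect).

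**Step 2: size of the shift if the confounder is left out.** Planned log odds ratio = ln[(0.81/0.19)/(0.70/0.30)] = ln 1.827 = 0.603. The shift is approximately d x ln(OR per SD). At d = 0.10:

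- OR 1.5: 0.1 x 0.405 = 0.041 (7% of 0.603)
- OR 2: 0.1 x 0.693 = 0.069 (11.5%)
- OR 3: 0.1 x 1.099 = 0.110 (18%)

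**Step 3: allow for the screen.** Imbalances that escape it tend to be smaller. The mean given a miss is d + SE x [φ(a) − φ(b)]/[Φ(b) − Φ(a)], with a = −1.96 − d/SE and b = 1.96 − d/SE. For d = 0.10 this is 0.061 SD (0.068 with the design effect). At OR 2 the shift is then 0.061 x 0.693 = 0.042 (or 0.047), 7 to 8% of 0.603. Averaged over flagged-and-adjusted and missed cases it is (1 − 0.437) x 0.0424 = 0.024, or (1 − 0.222) x 0.0473 = 0.037, which is 4 to 6%.

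**Step 4: scale.** The standard error of the log odds ratio is sqrt[1/(667 x 0.81 x 0.19) + 1/(633 x 0.70 x 0.30)] = 0.13, or 0.20 after multiplying the variance by 2.29. A shift of 0.069 is about half, or a third, of one standard error.

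**Step 5: site mix in Table 6.** Brigham and Women's/DFCI supplies 156/633 = 24.6% of controls and 104/667 = 15.6% of intervention women. Faulkner supplies 58/633 = 9.2% v 108/667 = 16.2%. Beth Israel Deaconess supplies 85/633 = 13.4% v 128/667 = 19.2%. The Brigham/DFCI gap is 0.0905/sqrt[(0.246 x 0.754 + 0.156 x 0.844)/2] = 0.0905/0.398 = 0.23 SD. A gap of that size would usually be flagged if site were among the variables compared; 12.3 does not say that it is.

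**The case against.** The strongest reply is that the plan is less data-driven than it first looks. A reader might infer that confounders enter only if they differ between groups. The text does not support that: race, language and insurance are in the model regardless of balance, and they are the factors on which the trial selects women as being at risk of delay. Nor does a flagged variable enter automatically; it is passed to a confounding assessment. The wording on further covariates can even be read as prior judgement about what might matter. All of this stands, and it limits the point to covariates beyond those three.

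A reader might also infer that the screen usually omits real confounders. That holds only below about 0.11 SD (0.165 SD with the design effect), and only under an assumed 0.05 test; larger imbalances are usually caught. Another tempting reading is that the reported confidence intervals would be too narrow. Nothing here shows that, and a screen on imbalance alone does not use the outcome. That the model would be settled after outcomes are known is likewise an inference, since 12.3 gives no timing.

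It can also be said that site and calendar time belong to the stepped-wedge model specification, and that 12.3 already commits to allowing for clustering. Handling correlation is not the same as a calendar-time term, however, and no such term is named. The gap remains.

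**Conclusion.** The point holds in limited form. Beyond race, language and insurance, selection for the primary logistic model rests on observed imbalance and apparent effect on the outcome, with no list, test or criterion; site and calendar time are unnamed although the arms differ on both. For one modest confounder the cost is small: at 0.10 SD and an odds ratio of 2 per SD, up to about 0.07 on a planned log odds ratio of 0.60, and about 0.04 to 0.05 on average when the screen misses it. Several omissions in the same direction could add up; the documents do not allow that total to be estimated. These sizes rest on the assumed test level and odds ratio, and the lower flag rates on applying the outcome design effect to covariates. The case for change rests as much on leaving the primary model unspecified in a largely historical comparison as on the size of any single shift. It should be changed, but it does not by itself undermine the trial.

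**What to change.** In 12.3, replace the imbalance-based selection with a prespecified covariate set for the primary logistic model: race/ethnicity, language, insurance, age at diagnosis, stage, hormone-receptor status, clinical site and calendar period. Define the period categories in the same place. Keep the balance table as description only, with no role in choosing the model.

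The cost is SAP wording and some loss of precision from the period terms. Diagnosis date, date of birth and institution are already requested for controls (10.1.5) and listed for chart abstraction. Age, stage and receptor status are needed to score the quality measures in 4.2.2, so their abstraction is implied. The control request in 10.1.5 lists neither stage nor receptor status and the abstraction form is not shown, so confirm that the form captures both for every woman before fixing the list.

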Design/Methodology:	We will conduct a stepped wedge hybrid effectiveness-implementation trial. The intervention proposed is a systems intervention. All subjects will be newly diagnosed breast oncology patients at one of the six participating clinical sites. In a stepped wedge design, sites are randomized to the time the site begins to implement the intervention and stratified by size. This will occur over an 18 month period, with a new site initiating the intervention every three months over this period. Historical data from each site serves as the comparison. Thus, 24 months prior to the time when the intervention begins at each site, women who meet the eligibility criteria will be given usual care (control) arm. Newly diagnosed cancer patients at the site after the time allocated to begin the intervention will be in the intervention arm. There will be no crossover.
Total Study Duration:	August 2018- July 2022
Subject Participation Duration:	Varies depending upon each patient's recommended cancer care as directed by their care team. Study participation will not influence the care recommended by the treatment team. Clinical outcomes will be collected from 0 to 24 months from the time of cancer diagnosis.

---

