### 5.1.2 Randomization scheme

Consistent with a stepped wedge design with one site implementing the intervention per step, prior to the collection of data in the pre-intervention period, a set of uniform random numbers has been generated for each of the six clusters to assign a starting period for the study intervention. There will be no crossover of patients from usual care to the intervention. That is, patients at each site during the pre-intervention period will experience only usual care and those enrolled after the initiation of intervention will experience the intervention.

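### With six randomised sites, section 12.3 fixes no site-level model, calendar-time term or small-sample correction, so the 0.05 alpha in 12.2 is not secured

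*Combined protocol and SAP*

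**What the plan says.** Section 12.2 sets the error rate: "Sample size estimates assume 80% power and a two-sided alpha of 0.05 for cross-sectional stepped wedge studies". It treats clustering as material, with "a reasonable ICC of 0.1, the design effect is 2.29", and concludes that "we will need to enroll and follow at least 1,008 subjects to provide 80% power".

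Sections 5.1.1 and 5.1.2 make the six sites the randomised units, with one site crossing over at each three-month step. On how the order was drawn, 5.1.2 says that "a set of uniform random numbers has been generated for each of the six clusters". The Protocol Summary (section 2) adds that sites were "stratified by size". Section 5.1.2 does not mention strata.

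Section 12.3 makes the primary analysis a multiple logistic regression of timely treatment start, adjusted for race, language, insurance and other covariates. Its whole provision for clustering in that analysis is that "we will employ statistical analytic methods that take the correlated nature of the data into account". It names no site term, calendar-time term, variance estimator, degrees of freedom or small-sample correction. The only correlated-data method it names is a GEE for missed appointments, where the cluster is the patient.

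**The concern.** Several standard analyses fit that sentence, and with only six clusters they do not behave alike.

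- **Sandwich (cluster-robust) standard errors** are built from six site-level residual contributions. They tend to be too small with so few sites, and a normal reference has tails that are too short.
- **Site fixed-effect and random-intercept models** avoid that problem. They do, however, assume that a site's effect stays the same throughout the study, here 21 quarters. Site-specific drift that is left out of the model makes their standard errors too small as well.

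An analyst could follow 12.3 to the letter and obtain a test close to 5% or one several times that. If the choice is made after the data are seen, it could decide whether the primary result is declared significant.

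**Working it through.** **1. The plan's own figure.** 2 × 220 × 2.29 = 1,007.6, which rounds to the stated 1,008. The inflation step reproduces. The 2.29 itself cannot be confirmed, because the enrolment per period behind it is not given. That does not matter for this point.

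**2. Inputs to the null simulation.**
- Six sites crossing in the Table 4 order, with a three-month wash-out each (5.1.1).
- Quarters: 21/3 + 18/3 + 24/3 = 7 + 6 + 8 = 21 (5.1.1).
- Site sizes from Table 6, 71 to 448, total 1,300.
- 70% timely in both groups, the usual-care rate in 12.2 ("81% in the intervention group compared to 70% in the usual care group").
- ICC 0.1 (12.2), with 0.05 as a check. Section 12.2 does not give the scale of its ICC.
- Assumption, not in the documents: the cluster autocorrelation (between-quarter divided by within-quarter correlation at a site) is 1, 0.8 or 0.5. A value of 1 means constant within-site correlation.

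**3. Rejection rates at nominal two-sided 0.05.** There were 2,000 trials per scenario. The Monte Carlo SE is √[p(1−p)/2000], about 0.5 points at 5% and 1.0 point at 27%. The first column covers ICC 0.1 and 0.05; the others are at ICC 0.1.

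| Analysis | Autocorr. 1 | 0.8 | 0.5 |
|---|---|---|---|
| GEE, uncorrected sandwich, z; no, linear or yearly time term | 15.5-19.8% | 17.2-18.4% | 16.9-19.1% |
| Same, quarterly time effects | 23.4-26.6% | 22.0-27.2% | 22.0-24.4% |
| Random-intercept logistic, z | 4.8-5.9% | 9.3-9.4% | 12.9-13.5% |
| Site fixed-effect logistic, z | 5.1-5.8% | 9.3-9.5% | 13.3-13.6% |
| Exchangeable GEE, model-based SE, z | 4.6-5.8% | 7.7-9.7% | 12.1-13.5% |
| GEE, Mancl-DeRouen SE, z | 6.0-10.4% | 6.8-10.7% | 6.1-11.5% |
| GEE, Mancl-DeRouen SE, t(5) | 2.3-4.8% | 2.8-5.0% | 2.8-5.8% |

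The random-intercept and site fixed-effect models were fitted with linear or yearly time terms only.

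**4. Effect of the reference distribution alone.** If a statistic follows t(5) but is compared with ±1.96, the error is P(|t₅| > 1.96) = 10.7%. For t(4) it is 12.2%. This is why the Mancl-DeRouen standard error needs the t reference.

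**5. Separate simulation.** This used Table 6 sizes, a calendar trend in the model and 2,000 runs. ICC 0.1 was read on the logit scale, giving a site SD of 0.605: 0.605² = 0.366, and 0.366/(0.366 + π²/3) = 0.366/3.656 = 0.100. The cluster-robust z test rejected in 16.5% and site fixed effects in 4.5%. With added site-by-quarter variation (assumed SD 0.3, 400 runs) the figures were 14% and 8.5%. The Monte Carlo SE at 14% is √(0.14 × 0.86/400) = 1.7 points.

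**6. Site dummies and the Mancl-DeRouen correction.** The correction inverts I − H for each site, where H is that site's block of the leverage matrix. With a dummy for every site, each block has an eigenvalue of 1, so I − H is singular. The two should not be combined.

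**7. Permutation test.** The number of possible orders limits the smallest p value. The block layouts are illustrations, not taken from the documents.
- Unrestricted: 6! = 720 orders, smallest p 1/720 = 0.0014.
- Two size strata of three, rolled out in blocks: 3! × 3! = 36, smallest p 1/36 = 0.028.
- Three strata of two, rolled out in blocks: 2 × 2 × 2 = 8, smallest p 1/8 = 0.125.

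**The case against.** The best defence is that 12.3 does promise to allow for correlation. A statistician might well choose a random intercept or site fixed effects, and both stay near 5% when within-site correlation is constant. The higher figures for those models rest on site-by-period variation that no section describes. This defence stands to the following extent: a reader might infer that the trial has a false-positive rate of 15-20%, and the documents do not support that. The range belongs to the uncorrected sandwich with a z test, which 12.3 does not select.

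Three further inferences also go too far.
- A reader might extend the six-cluster problem to the missed-appointments GEE. Its stated cluster is the patient, so the six-cluster argument does not apply to it as written.
- A reader might extend it to a Cox model with robust standard errors. Section 12.3 lists Cox regression for a secondary outcome without naming a robust variance, and no Cox analysis was simulated here.
- A reader might say that the Summary and 5.1.2 contradict each other on stratification. Section 5.1.2 is silent on strata. Random numbers for six sites could have been drawn within size strata.

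What the defence does not answer is that the promise in 12.3 excludes none of the poorly performing options.

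**Conclusion.** The concern holds as under-specification with a measurable consequence. Depending on a choice that 12.3 leaves open, the primary logistic test has a type I error of:
- about 15-20% with an uncorrected sandwich and z test, or 22-27% with quarterly effects;
- about 5-6% with site fixed effects or a random intercept, if within-site correlation is constant;
- about 8-14% with those models, if site-by-period variation is present but not modelled.

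The first range depends little on the assumed autocorrelation. The last depends on it entirely. All rest on the Table 6 projections and on reading the 12.2 ICC as a site random-intercept correlation. Confidence is medium. The change should be made because it is cheap and because one tested alternative kept the error between 2.3% and 5.8% in every scenario.

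**What to change.** State in 12.3, before outcomes are analysed, that the primary logistic model accounts for clinical site and calendar time. Give the form of the time term, and commit to one of these:

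- **(a)** a marginal (GEE) model with site as the cluster, a Mancl-DeRouen standard error and a t reference on about 5 df, without site dummies; or
- **(b)** a site fixed-effect or random-intercept model, with the p value from a permutation test over the site orders that the randomisation allowed.

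Option (b) has two preconditions. Document whether the size stratification in the Summary applied to the random numbers in 5.1.2, and confirm that the number of allowed orders permits p < 0.05. The permutation test was not simulated here. Because 5.1.1 excludes wash-out patients, 12.3 should also say how wash-out quarters are treated when the order is permuted.

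The cost is SAP wording and modest programming, with wider intervals and some loss of power. Under (a), the t(5) critical value of 2.571 against 1.960 widens intervals by 31% (2.571/1.960 = 1.31) even at the same standard error. Section 12.2 describes no allowance for this, so power should be rechecked under the chosen method.

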### **Hypothesis**

Our main hypothesis is that widespread implementation of these tools will eliminate care delivery disparities by reducing delays in time to first treatment. CTSA hubs have the translational expertise to overcome barriers to such implementation.

All participating sites currently provide patient navigation services, but none have evidence-based protocols, functional registries or social determinants of health platforms to support their patient navigation programs. As an integrated care delivery model, TRIP will benefit patients with breast cancer through individualized support and guidance. The only potential risk is a breach of confidentiality of data shared among the navigation network and the research team. This study will be conducted in compliance with the protocol, applicable regulatory requirements, and BMC/BU Medical Campus Human Research Protection policies and procedures.

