## 4 Objectives

### 4.1 Study Objectives

The main study objective is to conduct a stepped wedge hybrid effectiveness-implementation trial at six health systems (Beth Israel Deaconess Medical Center, Boston Medical Center, Brigham & Women's Faulkner Hospital, Dana-Farber Cancer Institute, Massachusetts General Hospital and Tufts Medical Center) in Boston caring for minority, non-English speaking and/or low-income women with breast cancer to assess clinical effectiveness and implementation of the integrated intervention (patient registry, Aunt Bertha SDOH platform, and patient navigation).

The primary objective is to test the clinical effectiveness of the intervention, as measured by the time to first cancer treatment and receipt of guideline concordant care. The secondary objective is to evaluate the implementation of the intervention (fidelity to intervention protocol).

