### 4.2 Study Outcome Measures

#### 4.2.1 Primary Outcome Measures

Our primary study outcome is ***Time to initiation of cancer treatment***, a continuous outcome defined as the number of days from diagnosis (Time 0) to treatment initiation (Time 1). Treatment initiation is defined as the time from biopsy until first treatment for cancer, either surgical, radiation, or systemic therapy. **Table 2** displays the specific data elements that will be used to define treatment initiation. As some patients have had pre-operative chemotherapy or hormone therapy, the time period will vary for each patient. This outcome has been widely used in existing navigation studies, as it has been linked to mortality and survival outcomes. Our study is powered on this clinical effectiveness outcome.

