## 4.2.2 Secondary Outcome Measures

Secondary clinical outcomes include select measures of **Guideline Concordant or Quality cancer care**, as defined jointly by the Commission on Cancer and the National Comprehensive Cancer Network. Specific measures of guideline concordant/quality care (yes/no) are defined in **Table 3**. These measures of quality will allow us to monitor initiation and completion of specific types of cancer therapy (radiation, chemotherapy and hormonal therapy) for different subsets of women.

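### Days to first treatment is the primary, powered outcome in 4.2.1 but a secondary outcome in 12.3, where the primary analysis is a logistic comparison of 'timely' treatment that has no day cut-off

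*Combined protocol and SAP*

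**What the plan says.** Section 4.2.1 names time to initiation of cancer treatment as the primary outcome, "a continuous outcome defined as the number of days from diagnosis (Time 0) to treatment initiation (Time 1", and adds: "Our study is powered on this clinical effectiveness outcome". The hypothesis in section 3.1 points the same way: the tools "will eliminate care delivery disparities by reducing delays in time to first treatment". Section 12.2 sizes the trial with a log-rank test, 220 per group, 81% against 70% treated at a time t that is not stated, a hazard ratio of 1.75, a design effect of 2.29 and a minimum of 1,008 patients.

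Section 12.3 reads differently: "Our primary analysis will use multiple logistic regression models to compare the proportion of patients with" timely initiation of treatment. The day count comes later: "Study groups will also be compared on the secondary clinical outcome of" time to initiation of primary cancer treatment, defined there as the number of days from diagnosis to start of treatment. It is to be analysed by Kaplan-Meier curves and by "Cox proportional hazards regression models controlling for cancer site and other covariates (adjusted analysis".

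Two other places bear on the hierarchy. Section 4.1 describes the primary objective "as measured by the time to first cancer treatment and receipt of guideline concordant care". Section 4.2.2 places guideline care lower: "Secondary clinical outcomes include select measures of" guideline concordant care.

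**The concern.** The same variable is primary in one section and secondary in another, so this is more than one outcome analysed in two ways. The endpoint that 12.3 puts in its place is not among the outcomes of section 4 or its tables, and no cut-off turns days into timely or not timely. Two analysts following 12.3 exactly could not be expected to produce the same primary result.

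At stake is control of type I error. If the choice between the two analyses, or the choice of cut-off, is still open when outcome data are seen, the nominal 5% no longer describes the false-positive risk. A second consequence is that the sample-size statement belongs to an analysis that 12.3 does not call primary.

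**Working it through.** **1. The sections side by side**

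| Place | Primary | Rank of days to treatment |
|---|---|---|
| 4.2.1 | Days from diagnosis to first treatment | Primary, powered |
| 12.2 | Log-rank test and hazard ratio; effect stated as proportions treated at t | Consistent with primary |
| 12.3 | Logistic regression on timely initiation | Secondary |

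The only day figure for first treatment is in 9.3.3: 60 days, beside 45 days for first surgery. Both are benchmarks for navigators using the registry, and nothing links them to an endpoint.

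**2. The plan's own total.** From 12.2: 2 x 220 x 2.29 = 1,007.6, so 1,008 is reproduced. The design effect of 2.29 is taken as given, because its inputs are not fully stated.

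**3. Size for the analysis 12.3 calls primary.** Pooled two-proportion formula with 0.70 against 0.81, two-sided alpha 0.05 and 80% power: 239 per group without continuity correction.
- Total: 2 x 239 x 2.29 = 1,094.6, about 1,095 (with continuity correction, 257 per group, about 1,178).
- Power at 1,008: 1,008/2.29/2 = 220 effective patients per group, about 77%.
- Power at 1,300 (633 and 667 from 5.1.4): effective sizes 633/2.29 = 276 and 667/2.29 = 291, about 86%.

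**4. Size for the log-rank analysis at the stated proportions.** Under proportional hazards, 81% against 70% treated implies a hazard ratio of ln(0.19)/ln(0.30) = 1.38, not 1.75.
- Events needed at 1.38: 304 (Schoenfeld) or 309 (Freedman).
- Mean proportion treated: (0.81 + 0.70)/2 = 0.755.
- Patients before clustering: 304/0.755 = 402.6 or 309/0.755 = 409.3, about 201 to 205 per group.
- Times 2.29: about 922 to 937 in total.

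So 220 per group does not follow consistently from its inputs. The nearest reconstruction, 217 per group, uses 1.75 and a 24.5% event rate, which would count untreated patients as the events.

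**5. What an open choice can cost.** Null simulations with no intervention effect compared a log-rank test (follow-up to 365 days) with a single 60-day test. Lognormal times, medians of 30 to 50 days and SD of log-time of 0.4 to 1.0 are assumptions.
- Independent patients, 633 v 667: each test alone 4.8% to 5.2%; either significant 7.7% to 8.4%.
- Six sites with Table 6 sizes, ICC 0.1 and site-stratified tests: each alone 4.9% to 5.4%; either significant 7.8% to 8.3%.
- If the cut-off may also be 30, 45 or 90 days (an illustrative set; median 40 days, independent patients): about 15% to 18%.

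All of these assume that the smallest p-value is reported and that there is no time trend.

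**The case against.** The best defence is that the hierarchy can be inferred. Section 4.2.1 is explicit, 12.2 uses a log-rank test, and the logistic model could be a loosely worded companion analysis. But 12.2 cuts both ways: it states the effect as a difference in proportions treated at a fixed time, which also resembles the binary endpoint. And 12.3 labels the day count secondary outright. Preferring days is reasonable, but it remains the sponsor's decision, and the document does not record it.

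Four stronger readings are tempting and are not supported:
- *The trial is underpowered.* Taking 2.29 as given for both analyses, 1,300 exceeds 1,095 and 937. Only the stated minimum of 1,008 falls short, and only for the binary analysis.
- *The protocol contains no day cut-off at all.* It gives 60 days for first treatment in 9.3.3; what is missing is a cut-off that defines the endpoint.
- *4.1 creates a second primary outcome.* An objective may name two measures, and 4.2.1 and 4.2.2 rank guideline care clearly enough. This is a minor point of alignment.
- *Cancer site is a meaningless covariate that should be deleted.* Tumour site is constant in this trial, but the protocol often uses 'site' for the hospitals, and a hospital term would matter.

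It is also fair that the 8% figure measures one pre-set cut-off and a worst-case choice. It shows what the text permits; it does not predict conduct.

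**Conclusion.** The contradiction stands in the current text and must be corrected: followed exactly, the plan yields two different primary results, one of them on an undefined endpoint. The open choice could raise type I error from 5% to about 8% with one 60-day cut-off, and further if the cut-off is also free, under the simulation assumptions above. The minimum of 1,008 does not serve the analysis that 12.3 calls primary (about 1,095 needed, about 77% power at 1,008), while the planned 1,300 is enough on either route. The size comparison assumes the same design effect for the binary and time-to-event outcomes, which the plan does not state. The hazard ratio of 1.75 is a separate error in 12.2 and does not decide which result is primary.

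**What to change.** Name one primary outcome and one primary analysis, in the same terms, in 4.2.1, 12.2 and 12.3.

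- *Route closest to 4.2.1 and 12.2:* in 12.3, make time to initiation of treatment primary and remove its secondary label. Keep the logistic analysis as supportive, with one day cut-off fixed before outcome data are analysed.
- *Alternative:* keep the binary outcome primary, state its cut-off, change 4.2.1 and restate 12.2 for that comparison (about 1,095 required, about 86% power at 1,300).

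On either route, the primary model should use the correlated-data methods that 12.3 promises and adjust for calendar time. Controls precede intervention patients at every site (section 5.1.1), so arm is confounded with period and allowance for clustering alone does not remove a secular trend. The price is some loss of precision. State what cancer site means in the Cox model.

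Separately, in 12.2, restate the hazard ratio, base size and total so that they agree: at 81% against 70%, about 1.38, 201 to 205 per group and 922 to 937 in total if the log-rank analysis is kept. When the text is next revised, also align the guideline-care wording in 4.1 with 4.2.2, and the follow-up limit (12 months in 5.1.6, 0 to 24 months in section 2).

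The cost is wording and a restated sample-size paragraph, with no new data or patients. The sponsor gives up the freedom to choose between endpoints and cut-offs later.
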